When the antihypertensive drugs are required dose reduction or interruption because of the concerns in tolerability with titration (i.e., excessive reduction in blood pressure, other AE, etc.) in the Treatment Period II, the antihypertensive drugs other than TAK-536 (in case of concomitant use) should be reduced or interrupted first. Thereafter, dose reduction or interruption of TAK-536 should be considered.

[figure not shown]
(4) Follow-up Period

Follow-up Period will be 2 weeks from the next day of the final dose of TAK-536. Safety will be evaluated at Week 54 after the start of the Treatment Period.

At the time when the data from approximately 25 subjects are collected, the data until Week 12 in the Treatment Period will be analyzed. In addition, at the time when all subjects complete Week 24 in the Treatment Period, the data until Week 24 in the Treatment Period will be analyzed separately after being locked. These analyses will not intend to continue or discontinue this study.

A schematic of the study design is included as Figure 6.a. A schedule of assessments is listed in Appendix A.

Figure 6.a Schematic of Study Design

- 1) The subjects whose blood pressures meet the inclusion criteria 1 (at earliest) week after receiving placebo in the Run-in Period can enter the Treatment Period. For the subjects only who treated with any antihypertensive drugs as a prior treatment only, the Run-in Period could be extended up to 4 weeks if blood pressures do not meet the inclusion criteria.
 - 2) If subjects have difficulty in discontinuing antihypertensive drugs completely at the start of the Run-in Period, the antihypertensive drugs can be down-titrated concurrently with administration of placebo. In the case of the down-titration, antihypertensive drugs should be discontinued at least 1 week (7 days) before the start of the Treatment Period I. Especially, beta-blockers (BBs) should be tapered off gradually since sudden discontinuation of BBs may cause withdrawal syndrome.
 - 3) In the Treatment Period I, TAK-536 can be titrated biweekly when the subjects do not achieve the target blood pressure while evaluation of safety and tolerability. TAK-536 can be reduced at the investigator's or subinvestigator's discretion if there are any concerns in tolerability with titration of TAK-536 (i.e., in case of occurring any AEs caused by titration of TAK-536).

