8.1.3 Dose and Regimen

During the Run-in Period, subjects will orally receive TAK-536 2.5 mg granules (placebo for the Run-in Period) if subjects weighing < 50 kg, or TAK-536 5 mg tablet (placebo for the Run-in Period) if subjects weighing ≥ 50 kg, once daily, before or after breakfast. During the Treatment Period, the same dose of the selected placebo during the Run-in Period will be the initial dose. After the initial dose, subjects will orally receive any of TAK-536 2.5 mg granules, TAK-536 5 mg, 10 mg, 20 mg tablet, once daily, before or after breakfast, if subjects weighing < 50 kg, or any of TAK-536 5 mg, 10 mg, 20 mg, 40 mg tablet, if subjects weighing ≥ 50 kg. For dose titration method, see Section 6.1 Study Design.

Because weight is likely to change during the study, the highest dose for the subjects is allowed to be changed if dose adjustment by changing of weight is required during the Treatment Period II.

The investigator or subinvestigator may select the timing of the study drug administration (i.e., before or after breakfast) in consideration of subject lifestyle but should not change this timing throughout the study. The investigator or its designee will record the guidance provided about the timing of the study drug administration (before or after breakfast) at the start of the Run-in Period (Week -2) in the eCRF.

At the start of the Run-in Period (Week -2), the study drug for the Run-in Period will be administered on the same day after completing all tests, observations, and evaluations. In case that

subjects take RAS inhibitors in the morning of the visit day, the administration of the study drug for the Run-in Period will be started from the next day.

Except for Week 16, subjects will visit the study site on each visit day without taking the study drugs, and receive them only after completing all tests, observations, and evaluations.

On the visit of Week 16, subjects, the subjects' parent or the subjects' legal guardian will be instructed to visit the study site after taking the study drug and the tests, observations, and evaluations 2 hour (acceptable time window, 1 to 3 hours) after taking the study drug will be performed.

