- Achievement of target blood pressure on each measuring day: Subjects are determined to have achieved their target blood pressures if their blood pressures are the < 95th percentile (both diastolic and systolic) shown in Table 5.a Reference Blood Pressure Values of Children by Gender and Age for essential hypertension or < 90th percentile (both diastolic and systolic) shown in Table 5.a Reference Blood Pressure Values of Children by Gender and Age for secondary hypertension. If either systolic or diastolic blood pressure is missing, it will be handled as missing data. The age at the time of informed consent will be used.

- Disease duration (years): (Date of informed consent [year and month] Time of onset [or diagnosis] of underlying disease [year and month]) / 12 (rounded to 1 decimal place) For the date of informed consent, only the year and month will be used. If the year of onset (or diagnosis) of underlying disease is unknown, it will be classified as "Unknown." If only the month of onset (or diagnosis) of underlying disease is unknown, the disease duration will be calculated with the month of onset (or diagnosis) of underlying disease as January.
- QTcF interval: Fridericia's formula (QT interval / [RR interval^{0.33}])
- CV (%): Standard deviation / mean × 100

7.1.2 **Definition of Study Days**

- Study Day: The day before the first study drug administration for the Treatment Period will be defined as Day -1 and the day of the first study drug administration for the Treatment Period will be defined as Day 1.
- Follow-up Day: The day after the last study drug administration for the Treatment Period will be defined as Follow-up Day 1.

7.1.3 **Definition of Study Visit Windows**

For each test, observation, and endpoint except for home blood pressure, all evaluable data (i.e., non-missing data) will be handled according to the following rules.

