For each visit other than the End of Treatment Period I and the End of Treatment Period, the evaluable data within the acceptable time window will be used. If more than one evaluable datum lies within the same acceptable time window, the data whose test/observation/evaluation time point is closest to the scheduled time point will be used. If there are two data equidistant to the scheduled time point, the data obtained later will be used. The temporal distance from the scheduled time point will be determined based on the Study Day and the time interval between the latest study drug administration and the blood sample collection.

For the End of Treatment Period I and the End of the Treatment Period, the evaluable data within the acceptable time window with the largest Study Day will be used.

Table 7.a Visit Window of Office Sitting Blood Pressure and Pulse Rate

Visit	Cahadulad Study Day	Acceptable Time Window	
Visit	Scheduled Study Day	Study Day	Follow-up Day
At the End of Run-in Period (Week 0)	Study Day: 1	-28 to 1	
Week 2	Study Day: 15	2 to 22	< 4
Week 4	Study Day: 29	23 to 43	< 4
Week 8	Study Day: 57	44 to 71	< 4
Week 12	Study Day: 85	72 to 99	< 4
Week 16 (postdose)	Study Day: 113	100 to 127	< 4
Week 20	Study Day: 141	128 to 155	< 4
Week 24	Study Day: 169	156 to 183	< 4
Week 32	Study Day: 225	184 to 253	< 4
Week 40	Study Day: 281	254 to 323	< 4
Week 52	Study Day: 365	324 to 372	< 4
Week 54 (Follow-up Period)	Study Day: 379	373 to 386	> 0
At the End of Treatment Period I*1		2 to 99	< 4
At the End of Treatment Period*2		2 ≤	< 4

^{*1} Data obtained after the earliest day of addition or dose change of antihypertensive drugs other than RAS inhibitors during the Treatment Period will not be used for summaries. Not applicable for office sitting pulse rate.
*2 The condition of *1 will not apply to this handling. Not applicable for office sitting pulse rate.

Table 7.b Visit Window of Clinical Laboratory Test Items

Visit	Scheduled Study Day	Acceptable Time Window	
V ISIL	Scheduled Study Day	Study Day	Follow-up Day
At the End of Run-in Period (Week 0)	Study Day: 1	-28 to 1	
Week 2	Study Day: 15	2 to 22	< 15
Week 4	Study Day: 29	23 to 43	< 15
Week 8	Study Day: 57	44 to 71	< 15
Week 12	Study Day: 85	72 to 99	< 15
Week 16 (postdose)	Study Day: 113	100 to 141	< 15
Week 24	Study Day: 169	142 to 225	< 15
Week 40	Study Day: 281	226 to 323	< 15
Week 52	Study Day: 365	324 to 379	< 15

Table 7.c Visit Window of Office Standing Blood Pressure and Pulse Rate

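### SAP Table 7.a can file a late Week 52 sitting BP or pulse reading as Week 54 follow-up and leave the true two-week reading unused

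*SAP*

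**What the plan says.** SAP 7.1.2 counts follow-up time from the last dose: "The day after the last study drug administration for the Treatment Period will be defined as Follow-up Day 1". The visit windows are in SAP 7.1.3. For office sitting blood pressure and pulse, Table 7.a has three relevant rows:

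- Week 52: scheduled Day 365, Study Day 324 to 372, Follow-up Day below 4.
- "Week 54 (Follow-up Period": scheduled Day 379, Study Day 373 to 386, Follow-up Day above 0, with no upper limit.
- End of Treatment Period: Study Day 2 or later, Follow-up Day below 4. Here "the evaluable data within the acceptable time window with the largest Study Day will be used". The footnote excludes pulse.

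If several readings fall in one visit window, "the data whose test/observation/evaluation time point is closest to the scheduled time point will be used"; in a tie, the later one is used.

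The other measurements have a later limit for Week 52. "Table 7.b Visit Window of Clinical Laboratory Test Items" and "Table 7.c Visit Window of Office Standing Blood Pressure and Pulse Rate" both run it to Day 379, as do Table 7.d (height and weight) and Table 7.e (ECG). None of these four tables has a Week 54 row.

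Protocol 6.1 says: "Follow-up Period will be 2 weeks from the next day of the final dose of TAK-536". Its next sentence places the safety evaluation at Week 54 counted from the start of treatment. On dosing, Protocol 8.1.3 says: "Except for Week 16, subjects will visit the study site on each visit day without taking the study drugs".

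**The concern.** The Week 54 row uses days since the first dose to identify a state defined by days since the last dose. Its only link to the last dose is that at least one day has passed. The treatment rows of the same table accept Follow-up Days 1 to 3 as on-treatment, so the two definitions overlap from Day 373 onward.

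SAP 7.8.2 lists Week 54 as an analysed visit for sitting blood pressure and target achievement, with confidence intervals and, for blood pressure change, a reference t-test. SAP 7.11.3 lists it for sitting pulse, which is one of the primary safety variables. Pulse has no End of Treatment Period summary, so a late on-treatment pulse would be reported only as follow-up.

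A reading on Follow-up Day 1 is about 24 hours after a dose. On the adult half-life of 12.8 hours in Protocol 6.2 that is 24 / 12.8 = 1.9 half-lives, whereas the protocol justified the follow-up length as five or more. A summary meant to describe children after treatment could thus contain on-treatment values and lack the genuine ones.

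**Working it through.** **Scheduled days.** Study Day = 7 × week + 1 gives 7 × 52 + 1 = 365 and 7 × 54 + 1 = 379. Both agree with Table 7.a.

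**Set-up.** Let L be the Study Day of the last dose. A reading on Follow-up Day k falls on Study Day L + k. With trough measurement and the last dose taken the day before, the final treatment reading is on Day L + 1. On schedule, L = 364, so the final reading is on Day 365, and Day 379 is Follow-up Day 379 − 364 = 15. Follow-up Day 14 is also checked, because a two-week visit could fall there.

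**Applying Table 7.a:**

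| Last dose (L) | Final reading (L + 1) | Rows it meets | Follow-up Day 14 / 15 reading | Week 54 value |
|---|---|---|---|---|
| 357 | 358 | Week 52, End of Treatment | 371 / 372 | none; both readings fit no row |
| 358 | 359 | Week 52, End of Treatment | 372 / 373 | Day 15 reading only |
| 364 | 365 | Week 52, End of Treatment | 378 / 379 | two-week reading, as intended |
| 371 | 372 | Week 52, End of Treatment | 385 / 386 | two-week reading, as intended |
| 372 | 373 | Week 54, End of Treatment | 386 / 387 | Day 373 |
| 374 | 375 | Week 54, End of Treatment | 388 / 389 | Day 375 |
| 385 | 386 | Week 54, End of Treatment | 399 / 400 | Day 386 |

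End of Treatment here means the End of Treatment Period row, which applies to blood pressure only.

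**Late end, L = 372.** Two readings can be eligible for Week 54. Day 373 is 379 − 373 = 6 days from schedule, and the Follow-up Day 14 reading is 386 − 379 = 7 days from it. The closest-day rule takes Day 373. A Follow-up Day 15 reading is on Day 387 and fits no row.

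**Late end, L = 373 or more.** The Follow-up Day 14 reading is on Day 387 or later and fits no row.

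**Final reading on Follow-up Day 2 or 3.** A reading on Day 373 to 386 again meets both rows. If L is 370 or 371, the two-week reading is still inside Day 386 and the outcome depends on the exact days. For example, with L = 371, readings on Day 373 and Day 385 are both 6 days away, and the tie rule keeps Day 385.

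**A dose taken on the late visit day.** The reading is not after the last dose, so it fails Week 54. It also fails Week 52 (after Day 372) and, for blood pressure, remains only as End of Treatment Period. L is then at least 373, so the two-week reading still falls after Day 386.

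**Early end.** L + 15 ≥ 373 needs L ≥ 358, and L + 14 ≥ 373 needs L ≥ 359. A two-week reading after an earlier last dose fits no row: it is before Day 373, and its Follow-up Day is not below 4.

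**No upper limit.** With L = 300, a reading on Day 373 to 386 would count as Week 54 at Follow-up Day 73 to 86.

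**Across tables.** A visit on Day 375 with L = 374 is Week 52 in Tables 7.b to 7.e and Week 54 in Table 7.a.

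**The case against.** The strongest reply is that the Study Day anchor follows the protocol, which also places the evaluation at Week 54 from the start of treatment, and that children on schedule are handled correctly. Both statements are right. A reader might infer that the SAP contradicts the protocol by using Study Day at all; the documents do not support that. The fault is narrower: a Study Day window with no effective lower limit on time since last dose overlaps what the same table calls on-treatment.

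A reader might also infer that every Week 52 visit after Day 372 is misfiled. It is misfiled only if the last dose was 1 to 3 days earlier. Protocol 8.1.3 has children dose after the tests and states no exception for Week 52; if a dose follows the reading, it is lost from Week 52 but not labelled follow-up.

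Nor does every child with an early last dose lose a reading. A Follow-up Day 15 reading after a last dose on Day 358 is kept, and Protocol 9.3.6 requires no follow-up tests when treatment stops at an early stage.

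The longer Week 52 windows in Tables 7.b to 7.e are not errors in themselves, since those tables have no Week 54 row to protect. Finally, the t-tests are for reference only, and the late blood pressure reading is still kept under End of Treatment Period. These points limit the effect; none removes the wrong label.

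**Conclusion.** The point holds as a labelling fault for off-schedule children. For a final trough reading on Day 373 to 386 with the last dose 1 to 3 days before, Table 7.a admits an on-treatment value to the follow-up summary. When the last dose was on Day 372 or later, it also leaves the two-week reading unused. Here on-treatment has the SAP's own sense of Follow-up Day below 4. At the early end, two-week readings are lost for last doses before Day 358 (Follow-up Day 15) or before Day 359 (Follow-up Day 14), where such readings were taken.

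The frequency cannot be computed. The documents give no visit-timing data, and the current protocol visit windows are not in the text available, so it cannot be said whether the protocol itself permits a Week 52 visit after Day 372. A reader might want to put a percentage on it; any such figure would be a guess. Each affected child is 1 of 50 planned, or 2% of a full by-visit summary, and a larger share within a weight group.

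The fault is confined to the Week 52 and Week 54 summaries of sitting blood pressure, target achievement and sitting pulse. The End of Treatment Period I analysis, to which the power statement refers, uses Days 2 to 99 and is unaffected. This is a minor correction.

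**What to change.** Change two rows of Table 7.a:

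- **Week 52:** Study Day 324 to 379 with Follow-up Day below 4, which matches the upper limit in Tables 7.b to 7.e.
- **Week 54:** define by Follow-up Day, with a lower limit of at least 4, an upper limit, and no Study Day limit. Centring on Follow-up Day 15 matches Day 379 for a child on schedule; 8 to 22 is one such range, since (8 + 22) / 2 = 15. Measure closeness from Follow-up Day 15.

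The two rows then cannot overlap. With the last dose on Day 374, the Day 375 reading becomes Week 52 and the reading on Day 388 or 389 becomes Week 54. A treatment reading after Day 379 would still have no by-visit row, as in Table 7.c, but would no longer be called follow-up.

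The SAP should also state whether the two-week readings of children who stop early are included in the Week 54 summary.

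The cost is two table rows and one sentence, with no change to data collection. The exact limits are a choice.

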7.1.4 Significance Level and Confidence Coefficient

• Significance level: 5% (2-sided test)

• Confidence coefficient: 95% (2-sided estimates)

No statistical testing and calculation of confidence interval will be performed if there are less than 2 subjects to be analyzed.

7.1.5 Conventions for Missing Adverse Event Dates

Not applicable in this study.

7.1.6 Conventions for Missing Concomitant Medication Dates

Not applicable in this study.

7.2 Analysis Sets

- Full analysis set (FAS): All subjects who received at least 1 dose of the study drug for the Treatment Period
- Safety analysis set: All subjects who received at least 1 dose of the study drug for the Treatment Period

7.3 Disposition of Subjects

7.3.1 Study Information

Analysis set:

All subjects who signed the informed consent form

Analysis variable(s):

Date the first subject signed the informed consent form

Date of last observation/test or contact, whichever comes later

MedDRA version

WHO Drug version

SAS version used for creating the data sets

Analytical method(s):

The following analysis will be performed for the above analysis variables.

(1) Display of analysis variables

7.3.2 Screen Failures

Analysis set:

All subjects who did not enter the Treatment Period

Analysis variable(s):

Categories in parenthesis [] (hereinafter, the same)

Age (years) [6, 7, 8, 9, 10, 11, 12, 13, 14, 15]

Gender [Male, Female]

Analytical method(s):

The following analysis will be performed for the above analysis variables.

(1) Frequency distributions for categorical variables and summary statistics for continuous variables

7.3.3 Subject Eligibility

Analysis set:

All subjects who signed the informed consent form

Analysis variable(s):

Entrance into the Treatment Period [Yes, No]

Primary reason for subject not entering the Treatment Period [Death, Adverse event, Screening failure, Protocol deviation, Lost to follow-up, Withdrawal by subject, Withdrawal by parent/guardian, Study terminated by sponsor, Pregnancy, Other]

Analytical method(s):

The following analysis will be performed for the above analysis variables.

When calculating the percentages for the primary reasons for subjects not entering the Treatment Period, the total number of subjects who did not enter the Treatment Period will be used as the denominator.

(1) Frequency distributions

7.3.4 Number of Subjects Who Entered the Treatment Period by Site

Analysis set:

All subjects who entered the Treatment Period

Analysis variable(s):

Entrance into the Treatment Period [Yes]

Stratum:

Study Site [Study site number is used for site classification]

Analytical method(s):

The following analysis will be performed for the above analysis variables by each stratum.

(1) Frequency distributions

7.3.5 Disposition of Subjects

Analysis set:

All subjects who entered the Treatment Period

Analysis variable(s):

Completed study drug for the Treatment Period [Completed, Prematurely discontinued]

Reason for discontinuation [Death, Adverse event, Protocol deviation, Lost to follow-up, Withdrawal by subject, Withdrawal by parent/guardian, Study terminated by Sponsor, Pregnancy, Lack of efficacy, Other]

Completed Follow-up Period [Completed, Prematurely discontinued]

Reason for discontinuation [Death, Adverse event, Protocol deviation, Lost to follow-up, Withdrawal by subject, Withdrawal by parent/guardian, Study terminated by Sponsor, Pregnancy, Lack of efficacy, Other]

Analytical method(s):

The following analysis will be performed for the above analysis variables by weight group ($< 50 \text{ kg}, \ge 50 \text{ kg}$) and in the combined weight groups. When calculating the percentages for the reasons for subjects not receiving the study drug, the total number of subjects who did not receive the study drug for the Treatment Period will be used as the denominator and when calculating the percentages for the reasons for discontinuation, the total number of subjects who prematurely discontinued will be used as the denominator.

(1) Frequency distributions

7.3.6 Study Drug Completion Status

Analysis set:

All subjects who entered the Treatment Period

Analysis variable(s):

Completed study drug for the Treatment Period [Completed, Prematurely discontinued]

Reason for discontinuation [Death, Adverse event, Protocol deviation, Lost to follow-up, Withdrawal by subject, Withdrawal by parent/guardian, Study terminated by Sponsor, Pregnancy, Lack of efficacy, Other]

Categories:

```
Duration of exposure to study drug for the Treatment Period (days) [0, 1 \le - \le 84, 85 \le - \le 168, 169 \le - \le 252, 253 \le - \le 336, 337 \le - \le 420, 421 \le - \le Max]
```

Analytical method(s):

The following analysis will be performed for the above analysis variables by weight group ($< 50 \text{ kg}, \ge 50 \text{ kg}$) and in the combined weight groups.

(1) Frequency distributions by duration of exposure to study drug for the Treatment Period

7.3.7 Protocol Deviations and Analysis Sets

7.3.7.1 Protocol Deviations

Analysis set:

All subjects who entered the Treatment Period

Analysis variable(s):

Protocol deviations [Deviations of protocol entry criteria, Deviations concerning excluded medication or therapy, Noncompliance with protocol, Deviations related to the treatment procedure or dose, Deviations of discontinuation criteria, Major GCP violations]

Analytical method(s):

The following analysis will be performed for the above analysis variables by weight group ($< 50 \text{ kg}, \ge 50 \text{ kg}$) and in the combined weight groups.

Frequency distribution of subjects with protocol deviations will be provided for above each deviation category. A subject who has several deviations that can be classified into the same category will be counted once in each appropriate category (overlapped counting).

(1) Frequency distributions

7.3.7.2 Analysis Sets

Analysis set:

All subjects who entered the Treatment Period

Analysis variable(s):

Handling of subjects in analysis sets [Categories are based on the specifications in Subject Evaluability List]

Inclusion/exclusion of analysis set

Full analysis set [Included]
Safety analysis set [Included]

Analytical method(s):

The following analysis will be performed for the above analysis variables by weight group ($< 50 \text{ kg}, \ge 50 \text{ kg}$) and in the combined weight groups.

For (1), a subject who falls into several categories will be counted once in each appropriate category (overlapped counting).

- (1) Frequency distributions concerning handling of subjects in each analysis set
- (2) Frequency distributions concerning number of subjects included in each analysis set

